### ***Unscheduled Clinic Visit***

- Unscheduled visits would be conducted for study participants with severe local or systemic reactions with assessment including vital signs, direct measurement of the extent of local reactions, and photographs of local reactions. Providers will be informed of the reactions in their patients and direct care as needed. Study staff will review the memory aid data (if applicable) and record any AEs, SAEs, concomitant medications, and current medical/pregnancy status as described in Section 5.1.

## **5.2 Treatment Assignment Procedures**

This is a pilot, open-label, prospective, randomized study involving pregnant women who are to receive Tdap and IIV vaccines. The specific vaccines administered are based on availability from manufacturers prior to the 2016-2017 and 2017-2018 influenza seasons.

### **5.2.1 Randomization**

Participants will be randomized (1:1) to receive either IIV and Tdap simultaneously or sequentially (IIV followed by Tdap) using a permuted block randomization scheme stratified by Lead and Contributing sites. The project statistician at Duke University will generate permuted block randomization schemes which will be uploaded to REDCap. The randomization schedule will not be available to the study staff, so the next randomization allocation will not be known before randomization occurs. Following confirmation of study eligibility criteria during Visit 1, participant randomization will be through REDCap with treatment allocation recorded on the CRF.

### **5.2.2 Blinding**

This study will be open label and study staff and subjects will not be blinded. Laboratory and pathology staff will be blinded to treatment arm assignment.

### **5.2.3 Vaccine Supply, Storage, and Administration**

In order to ensure adherence to study randomization assignment, US licensed IIV and Tdap vaccines will be administered as study procedures. Licensed Tdap and IIV (single dose vials or prefilled syringes) will be purchased for study administration and maintained at the study sites in a research-specific medication refrigerator at 2-8°C in accordance with package insert guidelines. Vaccine brand will be uniform across sites for both Tdap and IIV. The vaccine brands used for the study will be Boostrix® (GSK) [Tdap vaccine] and Fluzone Quadrivalent® (Sanofi) [influenza vaccine].

Pregnant women meeting eligibility criteria for the study will either receive 1) a single intramuscular (IM) 0.5 mL dose of IIV vaccine and single IM 0.5 mL dose of Tdap vaccine (simultaneous vaccination group) or 2) a single IM 0.5 mL dose of IIV vaccine followed by a single IM 0.5 mL dose of Tdap vaccine 22-29 days later (sequential vaccination group). Both vaccines will be administered by a licensed provider (RN, NP, PA, MD) following randomization assignment within the electronic data capture system. The study team will ensure that the vaccines will not be administered in the same arm. The vaccine manufacturer, lot number, expiration date, site of administration, and date/time of administration will be recorded on the case report form (CRF) and on the study product accountability log. Following administration, used study syringes will be disposed of according to standard operating procedure. Emergency management supplies will be available for initial treatment of an allergic reaction if needed.

The vaccine injection site(s) will be reviewed prior to subject leaving the clinic at least 20 minutes after vaccination takes place, which is consistent with current ACIP recommendations that individuals be observed for 15 minutes post-vaccination. The site(s) will be scored for evidence of local reactogenicity as listed below in **Tables 3 and 4**.

### **5.3 Reactogenicity Assessment**

Frequency and occurrence of local and systemic reactogenicity, solicited and unsolicited AEs, SAEs, concomitant medication use, and unscheduled medical care will be assessed immediately after vaccination (day 1) through post-vaccination Day 8 (day 1-8) using a standard memory aid (Appendix B-E). At the time of study enrollment, participants will be given an oral digital thermometer and instructed on completing the memory aid to document oral temperatures and post-injection symptoms, daily. A study staff member will review each portion of the memory aid with the subject in order to familiarize the subject with the form. The subject will be given the choice of either entering their data into REDCap daily or utilizing a traditional paper memory aid. Subjects will be instructed to notify study staff promptly using the 24-hour contact number provided in the memory aid in the event of any severe (Grade 3) local or systemic reactions.

Beginning on the evening of Study Visit 1 (Day 1) following vaccination, participants will record their oral temperature using the study-supplied thermometer, the occurrence of AEs, and concomitant medication use for the next 7 days (Day 1 – 8). Temperature will be recorded at roughly the same time each day. If a temperature  $\geq 100.0^{\circ}\text{F}$  ( $37.8^{\circ}\text{C}$ ) is recorded, a second measurement will be taken within 20 minutes. If more than one temperature is taken on the same day, the highest temperature should be recorded. Solicited adverse events (local and systemic), which will be classified as mild, moderate, or severe as described in **Tables 3 and 4**, will be reviewed and recorded during Visits 2-3 and 5-6.

Each day, women will record reactogenicity data either on paper or directly into the REDCap system through 7 days post-vaccination. All subjects will be provided with a paper memory aid (Appendix B-E) to record their reactogenicity data for ease of recall when entering into REDCap or recalling to research staff over the phone. We have selected a reactogenicity period of vaccination day and the next seven days based on pre-licensure studies of Tdap and IIV vaccines in adults and adolescents which suggest

that the onset of solicited, local adverse events is highest during days 1 through 4 post-vaccination. Moreover, pre-licensure data indicate a low incidence of late onset reactions (> 3 days post-vaccination). Contemporary evaluations of booster doses of both licensed Tdap vaccines (i.e., Boostrix and Adacel) have used either 4- or 7-day periods for assessments of reactogenicity citing that most local and systemic reactions occur within the first 48 hours after vaccination.

Women using REDCap will receive an email soliciting their record of events (daily link is sent via email for subjects to complete). The REDCap system provides real-time reports regarding who has responded. Local and systemic reactogenicity will be measured as described in **Tables 3 and 4** and subjects will contact the study team if they have any severe solicited symptoms or experience an SAE. AEs and SAEs will be reviewed in REDCap or by phone follow-up. For severe symptoms in REDCap, study team will follow-up with the subject by phone to gather more information about the symptoms.

Table 3: Injection-site Reactogenicity			
Symptom	Mild (Grade 1)	Moderate (Grade 2)	Severe (Grade 3)
Pain (without touching)	Noticeable but does not interfere with activity	Interferes with activity but did not necessitate medical visit or absenteeism	Prevents daily activity and/or resulted in medical visit and/or absenteeism
Pain upon touching (Tenderness)	Noticeable but does not interfere with activity	Interferes with activity but did not necessitate medical visit or absenteeism	Prevents daily activity and/or resulted in medical visit and/or absenteeism
Swelling (Induration)	<10 mm	10-34 mm	>=35 mm
Redness (Erythema)	<10 mm	10-34 mm	>=35 mm

Participants will also be queried during Visits 2-3 and Visits 5-6 on common post-vaccination local and systemic symptoms as described in **Tables 3 and 4**.

Participants using the paper diary will be contacted at Visits 2-3 and Visits 5-7 to review and document the information recorded in their diary. They will also be encouraged to report unsolicited adverse events in an open-ended question format, e.g. "How are you doing? Are you having any medical or clinical problems? If so, please tell me about them." Participants who report severe solicited adverse events or express any concern about symptoms/unsolicited events will be encouraged to follow up with their ObGyn or primary care provider. Study staff will assist with coordination of referral appointments as necessary. Medical records will be obtained and reviewed for any unscheduled medical appointment through post-vaccination Day 8. The same procedures for solicited adverse events will follow the second vaccination for the sequential group and be performed around the same time period for the simultaneous group in a "mock" fashion (Visits 4-6, with the exception of solicited injection site reaction). After Visit 4, solicited injection site reactions will not be recorded by participants in the simultaneous group. After the reactogenicity assessment period, only medically-attended adverse events will be collected.

Table 4: System Reactogenicity			
Systemic	Mild (Grade 1)	Moderate (Grade 2)	Severe (Grade 3)
Oral Temperature (°C/°F)**	≥ 37.8 - ≤ 38.7° C ≥ 100.0 - < 102.0 °F	≥ 38.8 - ≤ 39.4° C ≥ 102.0 - ≤ 103.0° F	≥ 39.5° C ≥ 103.1° F
Fatigue (Malaise)	Noticeable but does not interfere with activity	Interferes with activity but did not necessitate medical visit or absenteeism	Prevents daily activity and/or resulted in medical visit and/or absenteeism
Body Aches (Myalgia)	Noticeable but does not interfere with activity	Interferes with activity but did not necessitate medical visit or absenteeism	Prevents daily activity and/or resulted in medical visit and/or absenteeism
Headache	Noticeable but does not interfere with activity	Interferes with activity but did not necessitate medical visit or absenteeism	Prevents daily activity and/or resulted in medical visit and/or absenteeism
Chills/shivering (Feverishness)	Noticeable but does not interfere with activity	Interferes with activity but did not necessitate medical visit or absenteeism	Prevents daily activity and/or resulted in medical visit and/or absenteeism
Joint Pain (Arthralgia)	Noticeable but does not interfere with activity	Interferes with activity but did not necessitate medical visit or absenteeism	Prevents daily activity and/or resulted in medical visit and/or absenteeism
Nausea	Noticeable but does not interfere with activity	Interferes with activity but did not necessitate medical visit or absenteeism	Prevents daily activity and/or resulted in medical visit and/or absenteeism
Vomiting	Noticeable but does not interfere with activity	Interferes with activity but did not necessitate medical visit or absenteeism	Prevents daily activity and/or resulted in medical visit and/or absenteeism
Diarrhea	Noticeable but does not interfere with activity	Interferes with activity but did not necessitate medical visit or absenteeism	Prevents daily activity and/or resulted in medical visit and/or absenteeism
Abdominal Pain	Noticeable but does not interfere with activity	Interferes with activity but did not necessitate medical visit or absenteeism	Prevents daily activity and/or resulted in medical visit and/or absenteeism
Body Rash	Noticeable but does not interfere with activity	Interferes with activity but did not necessitate medical visit or absenteeism	Prevents daily activity and/or resulted in medical visit and/or absenteeism

\*\* Oral temperature, no recent hot/cold beverages or smoking

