## 5 STUDY SCHEDULE, PROCEDURES, & EVALUATIONS

### 5.1 Schedule of events

Pregnant women meeting the proposed eligibility criteria (Section 4.1-4.2) will be recruited. Written informed consent (Appendix I) will be obtained from study participants prior to conducting any study procedures. **Table 2** describes the proposed schedule of study visits with further details below.

Procedure	Screening Visit* Day -28 to 1	Visit 1 Day 1	Visit 2 Day 4 $\pm$ 1	Visit 3 Day 9 + 3	Visit 4 Day 22 + 7	Visit 5 Day 25 – 32 $\pm$ 1	Visit 6 Day 30 – 37 + 3	Visit 7 Day 43 -50 + 7	Visit 8 Delivery	Visit 9 Infant Blood Draw	Unscheduled Visit
Type of contact	Chart Abstraction/ Clinic	Clinic	Phone/ Email/ Text	Phone/ Email/ Text	Clinic	Phone/ Email/ Text	Phone/ Email/ Text	Clinic/ Phone/Email/ Text	Hospital/ Chart Abstraction	Clinic	Clinic
Informed consent & Medical Release of Information	X									X e	
Review Eligibility Criteria	X	X									
Review eligibility criteria for Tdap vaccination					X a						
Data Collection b	X	X	X	X	X	X	X	X	X		X
Influenza and Td/TT/Tdap Vaccination History	X										
Vital signs (temperature, heart rate, respiratory rate and blood pressure) c		X			X a						X

Collection of Cord Blood & Placenta									X		
Randomization		X									
Vaccination		X			X a						
Dispense and review instructions for Memory aid supplies & (REDCap or paper)		X			X						
Complete Memory aid form (REDCap or paper)		X	X	X	X	X	X				
Reactogenicity (local & systemic)			X	X		X	X				
Concomitant medications	X	X	X	X	X	X	X	X	X		X
Obtain solicited & unsolicited adverse events		X	X	X	X	X	X				X
Obtain medically-attended events and serious adverse events		X	X	X	X	X	X	X	X		X
Infant Data Collection d										X	
Infant Blood Sample (DBS)										X	
* Screening visit may occur simultaneously with Visit 1											
a Procedures for subjects in sequential group only											
b Data collection includes demographic information, medical and obstetric history, current pregnancy status. Changes in baseline medical status such as worsening or new onset condition will be capture as adverse events											
c Vital signs measured prior to vaccinations during Visit 1 and Visit 4											
d Data collection includes pertussis-specific medical history											
e Informed consent to be completed prior to Visit 9 blood draw											

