**Visit 6, Study Day 30 - 37 (window Days 30 – 40) Phone Call/Email/SMS Text Follow-Up**

Study staff will contact study participants (Appendix F) to review the memory aid data and record any AEs, SAEs, concomitant medications, and current medical/pregnancy status as described in Section 5.1. Participants who are lost to follow-up by phone contact will continue to be called on a weekly basis until approximately Day 45 following vaccination for safety assessment. Study staff will also approach participants at follow-up prenatal appointments which should be within 2-4 weeks based on routine prenatal care guidelines.

**Visit 7, Study Day 43 - 50 (window Days 43 – 57) Clinic Visit for sequential group, Phone Call/Email/Text for simultaneous group**

- This review will be done by phone call/email/text for study participants (Appendix F) in the simultaneous group and in clinic for participants in the sequential group. Study staff will review the memory aid data and record any AEs, SAEs, concomitant medications, and current medical/pregnancy status as described in Section 5.1. Obtain 15mL blood sample for serologic analysis for sequential group only (Section 6)

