### 7.1 Analysis Plan

**7.1.1 Study Populations** – There will be two study populations for this study. The Intent-to-Treat (ITT) and Safety populations. The ITT Population includes any participant that was enrolled and randomized into the study. The Safety Population is a subset of the ITT Population excluding those participants that never received the study intervention (either the influenza or Tdap vaccine). Statistical analyses will be performed for both study populations, or the ITT Population only if no participants are excluded for the Safety Population.

**7.1.2 Primary Objective 1** - To assess proportions of reactogenicity events in pregnant women receiving Tdap and IIV simultaneously vs. sequentially

Reactogenicity will be assessed for 7 days following each vaccination visit, as described in Section 5.3. The proportion of women and a 95% exact binomial confidence interval will be presented by treatment group, symptom, and grade level (mild/moderate/severe) for women with injection site reactogenicity within 7 days post-vaccination. This will be presented for each of the four reactogenicity outcomes, using the highest grade reported per woman. A 95% confidence interval of the difference in proportions between the treatment groups will also be presented. Systemic reactogenicity will be presented in a similar fashion. For adverse events, the proportion of women and a 95% exact binomial

confidence interval of adverse events, as well as the total number of adverse events, will be presented by treatment group, severity, and relatedness

**7.1.3 Primary Objective 2** - To assess maternal immune responses and cord blood antibody levels to pertussis antigens, tetanus and diphtheria toxoids, and influenza antigens in the women receiving Tdap and IIV simultaneously vs. sequentially

**7.1.3.1 Pertussis antigens** - Geometric mean titers (GMTs) will be calculated along with 95% confidence intervals for the two treatment groups for each pertussis antigen tested. A 95% confidence interval of the difference in GMTs between the treatment groups will also be presented.

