## Appendix F: Phone Script

## CISA TDAP/IIV Memory Aid Phone Script

To be used for visits: 2, 3, 5, 6, & 7

Hello, my name is \_\_\_\_\_ calling from the Tdap and Flu vaccine study at \_\_\_\_\_. I would like to review your memory aid information since your most recent study vaccination(s). This call should only take a few minutes. Is now a good time to review this information with you? Do you have your memory aid available to review with me?

Starting from day \_\_\_\_, please provide me with the temperatures that you recorded so far.

Starting with day \_\_\_\_, please tell me if you have recorded any reactions other than 0 (none). If so, in what category/ies? What number(s) did you record for the reactions? Did any of your symptoms prevent you from doing your daily activities or going to work/school?

Next on day \_\_\_\_, please tell me if you have recorded any reactions other than 0 (none). If so, in what category/ies? What number(s) did you record for the reactions? (*continue to ask for each day until all completed days have been reviewed with the subject*). Did any of your symptoms prevent you from doing your daily activities or going to work/school?

Did you report any other symptoms on your memory aid? Please provide me with the symptom, what you rated it, as well as the start and stop dates. (*continue to ask for any additional other symptoms*)

Did you take any new medications or change any of your current medications since you were vaccinated for the study? Please provide me with the medication name, dose, how often you took it, start and stop dates, and why you took the medicine.

Did you have any visits to the emergency room, urgent care, labor and delivery, or unplanned visits to the doctor's office, other than routine check-ups? If yes, please explain.

That concludes our study follow up call. Your next study visit is planned for: \_\_\_\_\_. Please remember to bring your memory aid with you to that visit so that we can place it in your study file.

Do you have any questions at this time? Please do not hesitate to contact the study team if you have any questions or concerns. We can be reached at \_\_\_\_\_.

Thank you for your continued study participation. Have a wonderful day.

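### Visit 7 has no single adverse-event scope and is held in clinic in one arm and remotely in the other, while Section 7.1.2 tabulates adverse events by arm with no time window

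*Combined protocol and SAP*

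**What the plan says.** The documents give two answers to what is collected once the second diary has ended.

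- **Restricted scope.** Section 5.3, closing its account of the second (real or mock) diary, says: "After the reactogenicity assessment period, only medically-attended adverse events will be collected". In Table 2 (Section 5.1), the row "Obtain solicited & unsolicited adverse events" is marked at Visits 1 to 6 and at unscheduled visits, but not at Visit 7. The row "Obtain medically-attended events and serious adverse events" is marked at Visits 1 to 8 and at unscheduled visits.
- **Unrestricted scope.** The Visit 7 text in Section 5.1 says: "Study staff will review the memory aid data and record any AEs, SAEs, concomitant medications, and current medical/pregnancy status". Section 5.3 itself has paper-diary users contacted at Visits 2-3 and 5-7 and encourages them, through an open question, to report unsolicited events. Footnote b of Table 2 also turns new or worsening conditions into adverse events under the data collection row, which is marked at Visits 7 and 8.

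The Visit 7 review is "done by phone call/email/text for study participants (Appendix F) in the simultaneous group and in clinic for participants in the sequential group".

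For the analysis, Section 7.1.2 takes the proportion of women with adverse events and its exact interval, "as well as the total number of adverse events, will be presented by treatment group, severity, and relatedness". It sets 7 days after each vaccination visit for reactogenicity. It sets no period for adverse events.

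**The concern.** Staff who follow the Visit 7 text record events that Section 5.3 and the adverse-event rows of Table 2 exclude. At that visit a sequential-arm woman sits with staff in clinic, while a simultaneous-arm woman answers by phone, email or text. Minor symptoms that never led to care are the events most likely to depend on who asks, how, and with what prompt. Staff and participants are unblinded (Section 5.2.2).

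Because Section 7.1.2 has no window, these events would be counted by arm alongside events gathered under matched conditions. A difference between the arms could then be produced or hidden by the mode of contact. Randomisation does not protect against this, because the difference arises after allocation. The table falls under Primary Objective 1, and the pilot is meant to inform a larger trial.

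**Working it through.** **Visit timing.** Inputs are Table 2 and the visit headings in Section 5.1. Write V4 for the study day of Visit 4, which lies between Day 22 and Day 29. These offsets reproduce the stated windows:

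| Visit | Offset from V4 | Earliest | Latest | Stated window |
|---|---|---|---|---|
| 5 | +2 to +4 | 22 + 2 = 24 | 29 + 4 = 33 | 24-33 |
| 6 | +8 to +11 | 22 + 8 = 30 | 29 + 11 = 40 | 30-40 |
| 7 | +21 to +28 | 22 + 21 = 43 | 29 + 28 = 57 | 43-57 |

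**Interval in dispute.** The second diary runs for eight days from Visit 4 (Appendices D and E), so it ends at V4 + 7.

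- End of second diary to Visit 7: 21 - 7 = 14 days at least, 28 - 7 = 21 days at most.
- Visit 6 to Visit 7: 21 - 11 = 10 days at least, 28 - 8 = 20 days at most.

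Both arms share these offsets, so the interval has the same length in each. What differs is how it is asked about.

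**Visit 7 by arm.**

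| | Simultaneous | Sequential |
|---|---|---|
| Mode | Phone, email or text | Clinic |
| Questions | Appendix F | Not clearly set: the visit text attaches Appendix F to the simultaneous arm only; the script's header lists Visit 7 without naming an arm |
| Scope, Visit 7 text | Any adverse event | Any adverse event |
| Scope, end of 5.3 and Table 2 adverse-event rows | Medically-attended and serious | Medically-attended and serious |

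**What is not affected.** Solicited systemic reactions in the diary weeks come from matching eight-day diaries in both arms (Appendices B to E). Injection-site reactions are recorded in the diary week after each actual vaccination. Medically-attended and serious events are collected in both arms through delivery (Table 2; Section 5.4), and the delivery record review covers maternal health events during pregnancy in both. That leaves unsolicited, non-medically-attended events first reported at Visit 7.

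**Scale.** About 80 women randomised 1:1 give 80 / 2 = 40 per arm. One more woman with an event, who would otherwise have none, moves an arm's proportion by 1 / 40 = 2.5 percentage points. This is the size of one woman's contribution, not an estimate of bias: the documents give no adverse-event rates and no data on reporting by mode of contact.

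**The case against.** The strongest reply is that little hangs on this. The primary outcome is the proportion of injection-site and systemic reactions, taken from diaries. For adverse events, Section 7.1.2 plans per-arm proportions with exact intervals and counts; the interval for a difference between arms is specified for reactogenicity, not for adverse events. Section 7 says that the pilot is not sized for group comparisons. The sequential arm's clinic visit has a purpose, the blood sample after Tdap. Randomisation is stratified by site, so a site that prefers one reading applies it to both its arms.

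All of this is correct, and it limits the point. It does not remove it: even within one site, following the Visit 7 text means asking the arms in different ways and putting the answers in a by-arm table that readers will compare.

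Two stronger inferences are tempting, and the documents do not support them.

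- **Different symptom recall periods by arm.** The opening line of Appendix F refers to the most recent study vaccination. That is Day 1 for the simultaneous arm and Visit 4 for the sequential arm from Visit 5 onward. A reader might infer that, at a Visit 5 call on Day 25 after Visit 4 on Day 22, one arm recalls 24 days and the other 3. But the symptom questions go through diary entries day by day, and the Visit 4 diaries cover the same eight days in both arms. The question on unplanned care has no anchor. Only the opening line and the medication question refer to vaccination. The longer anchor also adds no calendar coverage, because earlier contacts already asked about that time.
- **A 3.6-fold difference in observation.** A reader might set 57 study days against 16 diary days (57 / 16 = 3.6). That contrasts two readings of the protocol, each applying to both arms, and is not an arm difference. Nor is 16 days the period in Table 2, which also marks unsolicited events at Visit 4 and at unscheduled visits.

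**Conclusion.** The concern holds in a narrow form. The Visit 7 text conflicts with the last sentence of Section 5.3's adverse-event account and with the adverse-event rows of Table 2, and Section 5.3 is not consistent within itself. Because Visit 7 differs in mode by arm and Section 7.1.2 sets no window, unsolicited, non-medically-attended events first reported there would enter the by-arm table with arm-dependent ascertainment. It would be too strong to say that the adverse-event comparison as a whole is not like for like.

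Neither the direction nor the size of any bias can be derived from the documents. The conclusion assumes that staff follow the Visit 7 text as written, and that the reactogenicity period in the restricting sentence of Section 5.3 ends with the second diary, as its position and Table 2 suggest. It should be corrected, since the remedy is only wording, but it does not threaten the diary-based primary outcome.

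**What to change.** 1. **One scope for Visit 7.** Reconcile the Visit 7 text, both sentences of Section 5.3 (the restriction, and the open question at Visits 5-7) and Table 2, including footnote b. The natural choice is medically-attended and serious events only, as the restriction and the adverse-event rows already state.
2. **One set of questions.** Use the same scripted questions at Visit 7 in both arms, read out in clinic for the sequential arm.
3. **A window in Section 7.1.2.** Restrict the by-arm table of all adverse events to onset in the two matched 8-day periods: after Visit 1, and after Visit 4 or mock Visit 4. List separately any other unsolicited events, such as those recorded at Visit 4 or at unscheduled visits. Tabulate medically-attended and serious events separately through the end of follow-up.
4. **Minor wording in Appendix F.** For Visits 5 to 7, anchor the opening line and the medication question to the date of Visit 4 in both arms.

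The cost is edits to Sections 5.1, 5.3 and 7.1.2, Table 2 and Appendix F. The downside is that non-medically-attended events outside the two periods are listed if recorded, not compared by arm, and at Visit 7 they would no longer be sought.
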